Two subjects experienced SAEs: 1 SAE was reported in 1 subject who received a single dose of rhu-pGSN, and 2 SAEs were reported in 1 subject who received placebo in the multiple ascending dose phase. One subject who received a single dose of rhu-pGSN had an SAE of pneumonia (Grade 5, not related) after being withdrawn from the study; and 1 subject who received placebo had SAEs of pneumonia (Grade 4, not related) and pulmonary embolism (Grade 5, not related).

Pharmacokinetic analyses showed that the median rhu-pGSN half-life exceeded 17 hours with all dosing regimens. Overall, rhu-pGSN was well tolerated in patients admitted to non-ICU beds with CAP.

**Study BTI-202** was a Phase 2 randomized, double-blind, placebo-controlled study to evaluate the efficacy and safety of rhu-pGSN added to SOC for the treatment of subjects hospitalized with severe COVID-19 pneumonia (NCT04358406) (DiNubile et al., 2022). The study was conducted

in Spain and Romania. Sixty-four subjects with severe COVID-19 pneumonia were randomized 1:1 to receive rhu-pGSN or placebo intravenously in addition to SOC. Standard of care was left to the judgment of the caregivers without restrictions. Three doses of rhu-pGSN 12 mg/kg based on actual body weight were administered at 0, 12, and 36 hours. Of the 61 treated subjects, 54 completed the study, 4 died, and 3 were lost to follow-up. No subject discontinued due to an AE. The primary efficacy endpoint, the proportion of subjects alive without respiratory, hemodynamic, or renal support on Day 14, did not differ between treatment arms: 25 of 30 rhu-pGSN recipients (83.3%) and 27 of 31 placebo recipients (87.1%). Adverse events occurred with similar frequencies in both treatment groups. Most AEs were mild to moderate in severity and related to COVID-19 pneumonia. Serious adverse events were numerically fewer in the rhu-pGSN group than placebo group and all were assessed as unrelated to study drug. No pattern of AEs was discernable in either treatment arm. Two subjects in each group died during the 90-day study, but no deaths were attributable to study drug.

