### 3.5. Rationale for Study and Starting Dose

Given that pGSN is a naturally occurring plasma protein, the risk of drug toxicity related to rhu-pGSN infusion is expected to be low. In healthy primates dosed for 14 days, drug levels were similar to those obtained in human patients with pneumonia after administration of 12 mg/kg without evident toxicities. The doses given to humans have reached 24 mg/kg for 3 consecutive days. No distinctive safety signal was seen in the 2 small BioAegis studies to date; in fact, SAEs were numerically fewer in rhu-pGSN recipients compared to saline-placebo control subjects. However, in Study CBC-101 evaluating sick patients in the ICU administered a previous formulation of rhu-pGSN, 7 of 21 rhu-pGSN and 0 of 7 placebo recipients died ([Table 2](#)). None of the deaths were judged to be related to study drug and were all attributed to the serious underlying conditions of the participants. A post-hoc analysis indicated the rhu-pGSN group had higher acuity scores than the placebo group. All but one subject who died in Study CBC-101 were in the single-dose rhu-pGSN dosing groups.

Efficacy has only been demonstrated in animal models. It is anticipated that in sick patients, pGSN levels would be lower than normal at presentation and that rhu-pGSN administered IV would be consumed more rapidly than in healthy subjects. As such, efficacy in sick patients may require doses higher than used in the earlier clinical trials. Based on the previous human experience, 3 daily doses of 6, 12, and 24 mg/kg of rhu-pGSN were well tolerated in patients with CAP. An accelerated dosing schedule where rhu-pGSN was administered to patients hospitalized with COVID-19 pneumonia as 12 mg/kg at time 0, 12, and 36 hours was also generally well tolerated.

Before treating a larger number of critically ill patients to establish proof of concept in subjects with ALI/ARDS, the Sponsor aims to study the safety, tolerability, and PK of IV rhu-pGSN administered to healthy subjects. The current study is designed to primarily evaluate the safety and tolerability of sequential ascending doses of rhu-pGSN at 6, 12, 18, and 24 mg/kg of body weight, each given 5 times at 0, 12, 36, 60, and 84 hours.

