#### **4.1.2. Secondary Objectives**

- To characterize the pharmacokinetic (PK) profile of rhu-pGSN following administration of multiple (5) doses of rhu-pGSN to healthy subjects assigned to 4 dose levels (6, 12, 18, or 24 mg/kg)
- To investigate the development of anti-pGSN antibodies following administration of multiple (5) doses of rhu-pGSN administered to healthy subjects assigned to 4 dose levels (6, 12, 18, or 24 mg/kg)

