**Table 4: Schedule of Assessments**

	Outpatient	Inpatient	Inpatient	Inpatient	Inpatient	Discharge	Outpatient	Outpatient
Visit	Screening	Baseline/ Randomization /Treatment	Treatment/Follow-Up Days					EOS Visit
Day	-6 weeks to 0	1	2	3	4	5	7 ±1	28 ± 3
Informed consent	X							
Eligibility assessment	X							
Demographics	X							
Medical history	X							
Blood or urine pregnancy test a	X b							X
Physical exam (incl. height and weight)	X							
Vital signs c	X	X	X	X	X	X	X	
Blood/urine for safety laboratory analyses d	X b						X	X
Adverse events e		X	X	X	X	X	X	X
Review of Systems/Symptoms e	X	X	X	X	X	X	X	X
Study drug administration f		X/X (0 and 12 hours)	X (36 hours)	X (60 hours)	X (84 hours)			
Blood sampling for pGSN levels g		X (Dose #1)			X (Dose #5)	X (24 hours after Dose #5)	X	X

	Outpatient	Inpatient	Inpatient	Inpatient	Inpatient	Inpatient	Discharge	Outpatient	Outpatient
Visit	Screening	Baseline/ Randomization /Treatment	Treatment/Follow-Up Days						EOS Visit
Day	-6 weeks to 0	1	2	3	4	5	7 ± 1	28 ± 3	
Anti-rhu-pGSN antibody sampling		X							X
Concomitant medications	X	X	X	X	X	X	X	X	

Abbreviations: AEs=adverse events; ALT=alanine aminotransferase; aPTT=activated partial thromboplastin time; AST=aspartate aminotransferase; CBC=complete blood count; CPK=creatine phosphokinase; EOS=end of study; PK=pharmacokinetic; PT=prothrombin time

a Perform a serum or urine pregnancy test for female subjects unless they have had a hysterectomy.

b If performed more than 36 hours before initiation of study drug, the test must be repeated within this time frame.

c Record blood pressure, oral temperature, respiration rate, and heart rate. To be measured during infusions at the following time points: pre-infusion, every 15 minutes after the start of infusion, at the end of infusion, and 30 minutes after the end of infusion.

d Safety labs include collection of blood for a CBC, PT, aPTT, creatinine, bilirubin, alkaline phosphatase, CPK, AST, and ALT levels and collection of urine for drug screening (e.g., amphetamines, benzodiazepines, cannabinoids, cocaine, and opiates) and urinalysis (dipstick: glucose, protein, red blood cells, white blood cells).

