e Subjects will be interviewed to assess any possible AEs daily for 5 days, at 7 ± 1 day after Dose #1, and at 28 ± 3 days after Dose #1 (EOS Visit). Interviews can be done in person or by phone as mutually agreed by the Investigator and subject, but the EOS Visit should be done in person if possible so blood specimens can be collected.

f Study drug will be administered by IV infusion at time 0 (Day 1), 12 hours (Day 1), 36 hours (Day 2), 60 hours (Day 3), and 84 hours (Day 4). Dose 1 will be at time 0, and a window of ±2 hours will be allowed around dosing times for the 2nd and 3rd doses, and ±4 hours for the last 2 doses. Subjects are to be monitored for administration site reactions during an infusion and for 1 hour after its completion.

g Approximately 5 mL volume of blood will be drawn for measurement of pGSN levels on Day 1 within 30 minutes predose, and at 15 minutes and 1, 2, 4, 8, and 12 hours after Dose #1 and on Days 4 and 5 within 30 minutes predose, and at 15 minutes and 1, 2, 4, 8, 12, and 24 hours after Dose #5. Plasma will be obtained after centrifugation and promptly frozen at -20°C for assay in the central lab. A window of ±15 minutes will be allowed around the scheduled times except for the samples collected at 15 minutes postdose which have a window of ±5 minutes. A single sample will be collected anytime on Days 7 and 28.

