## **8.2. Measurement of pGSN Levels and Pharmacokinetic Assessments**

As indicated in [Table 4](#), approximately 5 mL volume of blood will be drawn for measurement of pGSN levels on Day 1 within 30 minutes predose, and at 15 minutes and 1, 2, 4, 8, and 12 hours after Dose #1 and on Days 4 and 5 within 30 minutes predose, and at 15 minutes postdose, and 1, 2, 4, 8, 12, and 24 hours after Dose #5. A window of  $\pm 15$  minutes will be allowed around the scheduled times except for the samples collected at 15 minutes postdose which have a window of  $\pm 5$  minutes. A single sample will be collected anytime on Days 7 and 28.

Plasma will be obtained after centrifugation and promptly frozen at  $-20^{\circ}\text{C}$  for assay in the central lab for analysis of pGSN concentrations. The concentration-time data will be used for the determination of PK parameters: maximum concentration ( $C_{\max}$ ), time to maximum concentration ( $T_{\max}$ ), terminal half-life ( $T_{1/2}$ ), area under the curve from time zero to 8 hours ( $\text{AUC}_{0-8}$ ), area under the curve from time zero to 12 hours ( $\text{AUC}_{0-12}$ ), and additionally after Dose #5, area under the curve from time zero to 24 hours ( $\text{AUC}_{0-24}$ ) and time zero to infinity ( $\text{AUC}_{\text{inf}}$ ).

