#### 10.1.2. Data Collection and Analysis

Baseline characteristics, safety, PK, and development of ADAs will be summarized via summary statistics separately for each rhu-pGSN dose level; data for all placebo subjects will be pooled. Additional details will be provided in a separate Statistical Analysis Plan (SAP).

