### **10.4.3. Pharmacokinetics and Immunogenicity**

$C_{max}$ ,  $T_{max}$ ,  $T_{1/2}$ ,  $AUC_{0-8}$ ,  $AUC_{0-12}$ , and additionally after Dose #5,  $AUC_{0-24}$  and  $AUC_{inf}$  will be calculated from the pGSN levels measured for Doses #1 and #5. Since the assay measures endogenous pGSN levels as well as exogenous recombinant pGSN, PK parameters will be calculated for values above baseline by subtracting predose pGSN level from each observed concentration. Tables and graphs will be provided.

Antibodies against rhu-pGSN will be assayed from frozen specimens to determine whether the investigational product induces an antibody response in recipients. The frequency of anti-pGSN antibodies with 95% confidence intervals will be provided for Day 1 (predose) and Day 28. If any subjects had antibodies at Day 1, the presence or absence of antibodies at Days 1 and 28 will be summarized in a  $2 \times 2$  table (Day 1 vs. Day 28).

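### Does leaving the predose sample unnamed in Section 10.4.3 put the Dose #5 pharmacokinetic results at risk?

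*Combined protocol and SAP*

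**What the plan says.** Section 10.4.3 lists Cmax, Tmax, T1/2 and partial AUCs for Doses #1 and #5, with AUC0-24 and AUCinf added after Dose #5. Because the assay cannot separate endogenous from recombinant pGSN, "PK parameters will be calculated for values above baseline by subtracting predose pGSN level from each observed concentration". The synopsis carries the same sentence. Neither place gives a day or dose number for the predose level.

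The sampling schedule provides two candidates. The first is drawn on Day 1 in the half hour before Dose #1. For the last dose, Table 4 footnote g schedules samples "on Days 4 and 5 within 30 minutes predose, and at 15 minutes and 1, 2, 4, 8, 12, and 24 hours", and Section 8.2 agrees: "on Days 4 and 5 within 30 minutes predose, and at 15 minutes postdose". Single samples follow on Days 7 and 28.

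In Table 4 only the Day 1 column carries a baseline label: "Baseline/ Randomization /Treatment". Section 10.1.2 adds that "Additional details will be provided in a separate Statistical Analysis Plan (SAP"; no separate SAP text on this point is in the documents reviewed.

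**The concern.** One of the secondary objectives is "To characterize the pharmacokinetic (PK) profile of rhu-pGSN following administration of multiple (5) doses", and Dose #5 is the only full profile taken after repeated dosing. The sample before Dose #5 comes about 24 h after Dose #4. For the pneumonia study, Section 3.4.2 reports that "the median rhu-pGSN half-life exceeded 17 hours with all dosing regimens", so a good deal of drug should still be circulating then. Section 3.5 expects that in sick patients "rhu-pGSN administered IV would be consumed more rapidly than in healthy subjects", which suggests that carry-over in volunteers would be no smaller.

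An analyst who corrected each profile by its own predose value would therefore remove study drug as well as endogenous protein. Dose #5 Cmax and AUCs would be understated, the terminal phase would be distorted, and AUCinf would rest on an unsound extrapolation. Anyone setting Dose #5 beside Dose #1 would see no accumulation where there was some.

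**Working it through.** The plan states no figure that depends on this choice, so there is nothing of its own to reproduce. The check has two parts: how large the error would be under the unfavourable reading, and which reading the text supports.

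**Inputs.** Dose times 0, 12, 36, 60 and 84 h (Section 4.1.1). Half-life 17 h, the bound from the pneumonia study (Section 3.4.2); 10 to 30 h is used as an assumed range. Further assumptions not in the plan: one-compartment linear kinetics with bolus input, and constant endogenous pGSN. Concentrations are in units of the rise produced by one dose.

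**Carry-over just before Dose #5.** With k = ln 2 / 17 = 0.0408 per hour,

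R = e^(-84k) + e^(-72k) + e^(-48k) + e^(-24k) = 0.033 + 0.053 + 0.141 + 0.376 = 0.603.

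**Dose #5 profile, t hours after the dose.**
- Day 1 value subtracted: (1 + R)e^(-kt). Only endogenous pGSN is removed, so the bias is 0.
- Dose #5 predose value subtracted: (1 + R)e^(-kt) - R.

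**Error under the second rule, 17 h half-life.**
- Cmax: R / (1 + R) = 0.603 / 1.603 = 38% too low.
- AUC0-12: 1.603(1 - e^(-12k))/k = 15.21; less 12 × 0.603 = 7.23 leaves 7.98, which is 48% too low. The Dose #1 AUC0-12 is 9.49, so the Dose #5 to Dose #1 ratio reads 7.98 / 9.49 = 0.84 instead of 15.21 / 9.49 = 1.60.
- AUC0-24: 24.53; less 24 × 0.603 = 14.47 leaves about 10.07, which is 59% too low.
- T1/2 fitted over 4 to 12 h: about 8 h instead of 17 h.
- Value at 24 h: 0.602 - 0.603, about zero.

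**Sensitivity.** For half-lives of 10 to 30 h, Cmax would be 19% to 55% too low and AUC0-24 39% to 72% too low. At 17 h, moving doses within the allowed windows gives R from 0.45 to 0.81, Cmax 31% to 45% too low, and a 24 h value between -0.13 and +0.09. A half-life fit that includes the 24 h point may therefore fail, or may run and be badly biased.

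**Would the error show?** Day 7 nominally falls 144 to 168 h after Dose #1, that is 60 to 84 h after Dose #5. With the ±1 day visit window this becomes 36 to 108 h. Under the second rule at 17 h:
- 36 h: 1.603e^(-36k) - 0.603 = -0.23
- 60 h: -0.46
- 84 h: -0.55
- 108 h: -0.58

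By Day 28 the drug has gone, and the corrected value would sit at about -0.60. A negative drug concentration in essentially every treated subject is not something a pharmacokineticist would pass over.

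**Which reading does the text support?** Three features agree. The reason given for subtracting is endogenous pGSN and nothing else. The result is described as lying above baseline. The schedule calls only Day 1 baseline. The sample before Dose #5 meets none of these, since it contains the drug that the analysis sets out to measure.

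**The case for a change.** The case for a change is that pointing to a sample is not the same as naming it. The schedule uses the same word, predose, for both samples; each profile has its own; and correcting a profile by its own predose value can be read literally from the sentence. The next paragraph of Section 10.4.3 does specify Day 1 when it describes the antibody analysis, so the day could easily have been given here as well. The two readings differ by more than a third in Cmax, and naming the sample would take one sentence.

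Some of this stands. The day is not named, no section defines baseline for pharmacokinetics, and the arithmetic is right on its assumptions. What does not stand is that the second reading is a live choice. It would make the subtraction remove the exogenous protein that the sentence distinguishes from the endogenous, and it would produce the impossible values shown above. The accumulation ratio is also not a listed parameter, although the endpoint wording leaves room for one. The choice of baseline sample is an ordinary detail for the separate SAP to which Section 10.1.2 defers.

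**Conclusion.** The wording is incomplete, but no change to the plan follows. Read by its stated purpose, the rule subtracts each subject's Day 1 level taken before Dose #1 from both profiles, and the bias is then 0% under the assumption of constant endogenous pGSN.

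The 38% (Cmax) and 59% (AUC0-24) understatements arise only if an analyst takes the sample before Dose #5 as baseline. They rest on one-compartment linear kinetics and on a 17 h half-life borrowed from patients with pneumonia. Even then the damage would be confined to descriptive secondary results for Dose #5, with six active subjects per dose level. Dose #1 parameters, the primary safety endpoint and the escalation decisions would be untouched, and the results could be recomputed from the Day 1 sample and the raw concentrations. Writing the day into the text would only record what a competent analyst would do anyway.

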## **11. DATA RECORDING, RETENTION AND MONITORING**

### **11.1. Case Report Forms**

Data will be collected using an electronic data capture (EDC) system at the clinical site. The Investigator or designee will record data specified in the protocol using eCRFs. Changes or corrections to eCRFs will be made by the Investigator or an authorized member of the study staff according to the policies and procedures at the site and the eCRF completion guidelines.

It is the responsibility of the Investigator to ensure eCRFs are complete and accurate. Following review and approval, the Investigator or designee will electronically sign and date the pages. This signature certifies that the Investigator has thoroughly reviewed and confirmed all data on the eCRF. Regardless of whether this responsibility has been delegated, the Investigator is personally responsible for the accuracy and completeness of all data included in the eCRF.

The Sponsor or designee will provide a portable document format (PDF) file of the eCRFs to the site for archiving after all data have been monitored and reconciled.

### **11.2. Records Retention**

Per Good Clinical Practice (GCP) guidelines regarding records retention, study documents are to be retained at the site until at least 2 years after the last approval of a marketing application in an International Council for Harmonization of Technical Requirements for Pharmaceuticals for Human Use (ICH) region or at least 2 years have elapsed since the formal discontinuation of clinical development of study drug. The Sponsor will notify the site of the date when study documentation may be destroyed.

### **11.3. Data Monitoring**

This study will be closely monitored by representatives of the Sponsor throughout its duration. Monitoring will include personal visits with the Investigator and study staff as well as appropriate communications by telephone, fax, mail, email or use of the EDC system, if applicable. It is the responsibility of the monitor to inspect eCRFs at regular intervals throughout the study to verify the completeness, accuracy and consistency of the data and to confirm adherence to the study protocol and to GCP guidelines. The Investigator agrees to cooperate with the monitor to ensure that any problems detected during the course of this study are resolved promptly. The Investigator and site will permit study-related monitoring, audits, IEC review and regulatory inspection, including direct access to source documents.

It is understood that study monitors and any other personnel authorized by the Sponsor and/or Sponsor representatives may contact and visit the Investigator and will be permitted to inspect all study records (including eCRFs and other pertinent data) on request, provided that subject confidentiality is maintained and that the inspection is conducted in accordance with local regulations.

Every effort will be made to maintain the anonymity and confidentiality of subjects during this study. However, because of the experimental nature of this treatment, the Investigator agrees to allow representatives of the Sponsor as well as authorized representatives of regulatory authorities to inspect the facilities used in the conduct of this study and to inspect, for purposes of verification, the hospital or clinic records of all subjects enrolled in the study.

#### **11.4. Quality Control and Quality Assurance**

The study site may be audited by a quality assurance representative of the Sponsor or its designee for the purpose of monitoring any aspect of the study. The Investigator agrees to allow the monitor and/or auditor to inspect the drug storage area, study drug stocks, drug accountability records, patient charts and study source documents, and other records relative to study conduct.

The Investigator should contact the Sponsor or designee immediately if contacted by a regulatory agency about an inspection.

## **12. REGULATORY, ETHICAL AND LEGAL OBLIGATIONS**

### **12.1. Good Clinical Practice**

The study will be performed in accordance with the protocol, guidelines for GCP established by the ICH, and applicable local regulatory requirements and laws.

### **12.2. Independent Ethics Committee Approval**

The Investigator must inform and obtain approval from the IEC for the conduct of the study at named sites, the protocol, informed consent documents and any other written information that will be provided to the subjects and any advertisements that will be used. Written approval must be obtained prior to recruitment of subjects into the study and shipment of study drug.

The Investigator is responsible for informing the IEC of any amendment to the protocol in accordance with local requirements. Amendments may be implemented only after a copy of the approval letter from the IEC has been transmitted to the Sponsor. Amendments that are intended to eliminate an apparent immediate hazard to subjects may be implemented prior to receiving Sponsor or IEC approval. However, in this case, approval must be obtained as soon as possible after implementation.

Per GCP guidelines, the Investigator will be responsible for ensuring that an annual update is provided to the IEC to facilitate continuing review of the study and that the IEC is informed about the end of the study. Copies of the update, subsequent approvals and final letter must be sent to the Sponsor.

### **12.3. Regulatory Authority Approval**

The study will be performed in accordance with regional regulatory requirements and will also meet all of the requirements of ICH GCP guidance. Amendments to the protocol will be submitted to the appropriate regulatory agency/agencies prior to implementation in accordance with applicable regulations.

